### 5.2 Rationale for study design

The Diabetes Pregnancy Registry is specifically designed to monitor and assess the safety of the use of Levemir® in pregnant women and the health status of their infants until 1 year of age. Every diabetic woman treated with insulin or other injectable antidiabetic treatment regimens and who has not changed basal insulin or other injectable antidiabetic treatment product (for those not treated with basal insulin) 4 weeks prior to and following conception is eligible for enrolment. Thus, the

registry constitutes a unique opportunity for large -scale data collection that will allow comparisons and analysis between the injectable antidiabetic treatment regimens in pregnant women with DM.

The Diabetes Pregnancy Registry will be based on prospectively collected clinical data as part of the normal clinical practise in pregnancy. The database will be established as part of present standard clinical practice used in the treatment of pregnant women with DM at the selected study sites. A panel of the study sites enrolled in the Novo Nordisk Levemir® pregnancy trial (NN304-1687) were contacted prior to inclusion in the registry, and asked to fill out a flow chart illustrating the specific standard routine procedures at their specific clinic. The standard routine procedures used with regard to the treatment of diabetic women during pregnancy are almost similar between the included study sites resulting in a uniformed treatment procedure and furthermore, these study sites have a relatively high prescription rate of Levemir®.

The prospective non-interventional study design in a large-scale setting is needed to ensure a sufficient number of patients in order to have an adequately powered study to analyse the safety of Levemir® with regard to the primary and secondary endpoints in a real-world population of diabetic pregnant women and their infants.

The collected data will constitute the Diabetes Pregnancy Registry data set.

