#### 3.1 Basic information

The use of insulin analogues has increased significantly in the treatment of both type 1 and type 2 diabetes mellitus (T1DM and T2DM, respectively). Insulin analogues are used in pregnant women with diabetes, as this group has a particular requirement for the safe and efficacious treatment that insulin analogues can deliver. As pregnancy in women with DM is associated with an increased risk of complications for both the mother and the foetus/new-born especially if glycaemic control is outside the target, and as the treatment needs to be adjusted during pregnancy, it is considered a medical challenge to ensure that these women receive the most optimal glycaemic control without inducing hypoglycaemia. If pregnant women receive optimal treatment, it will both increase their own well-being and reduce the overall risk of diabetes complications and pregnancy complications both for the mother and the child. Complications associated most frequently with pregnancies in women with DM include the following :

- Major hypoglycaemia
- Progression of maternal diabetic complications
- Spontaneous abortion
- Pre-eclampsia and pre-term delivery
- Perinatal and neonatal death
- Congenital malformations
- Foetal macrosomia

During recent decades, pregnancy outcomes in women with DM have improved considerably. Hypo- and hyperglycaemia remain, however, a major challenge in the treatment of pregnant women with DM. The proportion of pregnant women reporting major hypoglycaemic episodes that require third party help is as high as 71% . Of these, 33–41% of the episodes additionally require parenteral glucose or glucagon.

The rate of pre-eclampsia in pregnancies in women with DM increases with advanced maternal age, poor glycaemic control and baseline proteinuria . The literature is inconsistent in particular with respect to the rate and severity of pre-eclampsia, but the minimum risk reported in women with DM is 10% .

The most common organs affected by malformations are the central nervous system, heart, skeleton, kidneys, gastro-intestinal tract and lungs. The prevalence of major congenital anomalies in infants of women with DM was 4.5% in a population-based study in England, Wales and Northern Ireland

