[11](#) and the results are in line with results from a nationwide prospective Norwegian study from 2010 [12](#). In addition, infants of women with DM are 5 times more likely to be stillborn and 3 times more likely to die in their first month of life (neonatal death) compared with those of mothers without DM [11](#). The perinatal death risk is approximately 3% and the neonatal death risk is 0.9% [11](#) and comparable with rates from other European countries [11,13-17](#). Finally, foetal macrosomia is reported to occur in 25–30% and in some studies in more than 40% of the new-borns to mothers with DM [5,7](#).

Pregnant women with DM and with good metabolic control are not more likely than non-diabetic women to lose a pregnancy. This is in contrast to a risk of 15–26% of having a spontaneous abortion in the first trimester for diabetic women who have elevated blood glucose levels [3,8,9](#). As increased perinatal and neonatal death, morbidity and a 2–5-fold increase in congenital anomalies compared with the general population are reported in pregnant women with DM [2](#), further data on the effects of treatment on pregnant women with DM are needed.

Levemir® was approved for treatment of pregnant women with DM in the EU in 2011 [18](#).

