### 14.1 Sample size calculation

The sample size calculation is based on the combined primary endpoint, which is to compare the proportion of pregnancies in pregnant women treated with Levemir® to pregnant women treated with other basal insulin regimens which results in none of the 3 individual outcomes: major congenital malformations, perinatal and neonatal death.

Due to new knowledge obtained after study initiation regarding the observed split between treatment groups and pregnancy outcome incidence, a revised sample size calculation has been performed that takes the differences from the original assumptions into account. The original and revised sample size calculations are described in Sections 14.2 and 14.3, respectively.

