### 14.2 Original sample size calculation

The following proportions are assumed for each of the individual outcomes as described in section [3.1](#):

- Major congenital malformations: 4.5%
- Perinatal death: 3%
- Neonatal death: 0.9%

[figure not shown]
The probability of the combination of the endpoints is not known in the literature but the proportion of pregnancies with any of the above outcomes will be estimated at 8.2% as described below. This combined probability is computed under the assumption that the individual outcomes are independent.

The primary endpoint is the proportion of pregnancies without any of the above outcomes. The proportions of patients not getting any of the outcomes is assumed to be:

- Major congenital malformations:  $1 - 0.045 = 0.955$
- Perinatal death:  $1 - 0.03 = 0.97$
- Neonatal death:  $1 - 0.009 = 0.991$

None of the outcomes:  $0.955 \times 0.97 \times 0.991 = 0.918$ , i.e. 91.8% of patients are expected not to get any of the pregnancy outcomes above, and  $100\% - 91.8\% = 8.2\%$  are expected to get one of the outcomes.

The sample size calculation is based on the assumption that the proportion of pregnancies without the combined pregnancy outcome is 91.8% in the Levemir® group or the other basal insulin regimens group. The goal is to be able to detect a difference of 3.5% between the proportions without the combined endpoint in the Levemir® group compared to the other basal insulin regimens group. Assuming a maximum 1:2 split between the two groups, a sample size of 1,833 pregnancies is needed in order to have 80% power of achieving significance at 5% level (see [Figure 14-1](#)).

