### 14.3 Revised sample size calculation

A revised sample size calculation has been performed based on a 1:1 split between the number of subjects treated with Levemir® and the number of subjects treated with other basal insulin products and a more realistic pregnancy outcome incidence, while keeping the other assumptions identical to those used in the original sample size calculation.

[Figure 14-2](#) shows the revised sample size calculation based on a 1:1 split between the groups and pregnancy outcome incidences ranging from 92% to 96%. As indicated in the figure, a total sample size of 1222 (based on a 1:1 split including 611 subjects treated with Levemir® and 611 patients on other basal insulin regimens) will be sufficient to be able to detect a difference of 3.5% in the primary endpoint measure when the proportion of pregnancies resulting in none of the 3 pregnancy outcomes is  $\geq 93.5\%$ .

This sample size of 1222 is likely to be sufficient, even if the proportion of pregnancies resulting in none of the 3 pregnancy outcomes, unexpectedly, will be lower than the currently observed (97.3% observed versus 91.8% originally assumed).

**Figure 14-2 Total sample size sufficient to detect a minimal clinically relevant difference of 3.5% for proportion of pregnancies without the combined pregnancy outcome ranging from 92-96% (assuming a 1:1 split between the Levemir® group and the other basal insulin regimens group).**

When calculating the number of subjects to be enrolled in the study, it has to be taken into account that not all subjects will be included from the primary analysis. The percentage of enrolled subjects, which are to be excluded from the primary analysis is approximately 40% and thereby in line with the original assumption used for the sample size calculation. Therefore, the sample size has been adjusted to  $1222 / (1 - 0.40) = 2037$  (as a minimum) subjects to be enrolled in the study.

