For the infants endpoints at 1 year of age the proportions will also be analysed using logistic regression, the model will include treatment group (Levemir®/other basal insulins group), study site, race, hypertension, major hypoglycaemic events during pregnancy, folic acid intake, and possible use of GLP-1 agonists during pregnancy as factors. Furthermore, HbA1c at start of pregnancy, end of first trimester, and end of second trimester, age and BMI of the woman at baseline, duration of DM, blood pressure and previous foetal pregnancy complications will be included as covariates. The analyses regarding height and weight will also be adjusted for exclusive and/or partial lactation period.

The means of the continuous endpoints (maternal HbA1c at the end of each trimester and, height and weight of the infant at 1 year), will be compared between the Levemir® group and the other basal insulins group using an analysis of covariance (ANCOVA) model.

The incidence of major hypoglycaemia during pregnancy will be computed for both treatment groups.

Additional exploratory hypothesis-generating analyses may also be performed as deemed relevant.

Differences in gestational age at study entry and exact follow-up time will be taken into account in the statistical analysis where relevant.

All statistical analyses will be performed using appropriate statistical software. All statistical tests will be performed as two-sided tests with a significance level of 0.05.

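### Section 5.2 claims adequate power for the secondary endpoints, but the sample size is derived for the primary composite only and no secondary effect size or power is given

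*Protocol*

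**What the plan says.** Section 5.2 (Rationale for study design) justifies the large-scale setting as necessary "in order to have an adequately powered study to analyse the safety of Levemir ® with regard to the primary and secondary endpoints".

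Section 14.1 names the basis of the calculation: "The sample size calculation is based on the combined primary endpoint". Section 14.2 sets the target, "80% power of achieving significance at 5% level", for a 3.5-point difference in the composite, and arrives at 1,833 pregnancies with a 1:2 split. Section 14.3 revises this to 1,222 (611 per group), "while keeping the other assumptions identical to those used in the original sample size calculation", and concludes that this number "will be sufficient to be able to detect a difference of 3.5% in the primary endpoint measure" when the event-free proportion is at least 93.5%. Section 6.1 divides 1,222 by 0.60 to reach a minimum enrolment of 2,037.

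Section 14.4 applies the primary analysis (difference, 95% confidence interval, Fisher's exact test) to every other endpoint that is a proportion, and adds: "All statistical tests will be performed as two-sided tests with a significance level of 0.05". Background rates for several secondary outcomes are in section 3.1. The summary lists pre-eclampsia, perinatal death and neonatal death among the key secondary endpoints. Macrosomia is secondary but not key.

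**The concern.** The two statements do not fit together. Section 5.2 asserts a property for two families of endpoints, and section 14 demonstrates it for one. Power has no meaning without an effect size, and none is stated for any secondary endpoint. The revision from 1,833 to 1,222 pregnancies was argued from composite inputs alone (the split between groups and the composite's incidence), yet 5.2 still claims power for the secondary endpoints.

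Section 5.1 describes the study as a post-authorisation safety commitment to the European regulator. A reader who trusts 5.2 could take a non-significant result on a rare outcome such as neonatal death as more reassuring than 611 pregnancies per group can make it.

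**Working it through.** **Inputs**
- Two-sided alpha 0.05 and Fisher's exact test (14.4); power target 80% (14.2, carried into 14.3).
- 611 per group (14.3).
- Rates from 3.1: pre-eclampsia 10% (described as the minimum reported), macrosomia 25% (low end of 25–30%), perinatal death 3%, neonatal death 0.9%.
- Effect sizes: assumed. Scenario A borrows the composite's 3.5 points. Scenario B is a doubling, which is my choice.

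**Formula.** Power = Σ Σ Bin(x₁; n₁, p₁) · Bin(x₂; n₂, p₂) over all pairs (x₁, x₂) with Fisher p ≤ 0.05. The Fisher p-value sums the probabilities of all tables, given the margins, that are no more likely than the one observed.

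**Reproducing the plan's figures**
- Revised: 611 vs 611, 93.5% vs 97.0% event-free gives 79.9% (stated target 80%).
- Original: 1,222 at 91.8% vs 611 at 95.3% gives 80.3%.
- Enrolment: 1,222 / 0.60 = 2,036.7, so 2,037.

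The plan's arithmetic for the composite is reproduced, taking the difference as an improvement on the stated proportion.

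**Scenario A: 3.5 points, 611 per group**

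| Endpoint | Comparison | Power |
|---|---|---|
| Pre-eclampsia | 10 vs 13.5% | 44% |
| Pre-eclampsia | 10 vs 6.5% | 57% |
| Macrosomia | 25 vs 28.5% | 26% |
| Macrosomia | 25 vs 21.5% | 28% |
| Perinatal death | 3 vs 6.5% | 80% |
| Neonatal death | 0.9 vs 4.4% | 97% |

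The perinatal figure equals the composite's because 3 vs 6.5% is 97 vs 93.5% read from the other side. The neonatal comparison is a ratio of 4.4 / 0.9 = 4.9.

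**Scenario B: doubling, 611 per group**

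| Endpoint | Comparison | Power |
|---|---|---|
| Pre-eclampsia | 10 vs 20% | above 99% |
| Macrosomia | 25 vs 50% | above 99% |
| Perinatal death | 3 vs 6% | 68% |
| Neonatal death | 0.9 vs 1.8% | 20% |

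A tripling of neonatal death (0.9 vs 2.7%) has 60%.

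**Hand check with the pooled normal approximation, 10 vs 13.5%.** The mean proportion is 0.1175. The null standard error is √(2 × 0.1175 × 0.8825 / 611) = 0.01842, and the alternative one is √((0.10 × 0.90 + 0.135 × 0.865) / 611) = 0.01840. Power = Φ((0.035 − 1.96 × 0.01842) / 0.01840) = Φ(−0.06) = 48%, a little above Fisher's 44%, as expected.

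**Smallest increase with about 80% Fisher power, 611 per group**
- Pre-eclampsia: 10% to about 15.5% (79.0% at 15.4, 80.4% at 15.5).
- Perinatal death: 3% to about 6.5% (79.9%).
- Neonatal death: 0.9% to between 3.2% (78.3%) and 3.3% (81.2%), about 3.6-fold.
- Macrosomia: 25% to about 32.4% (80.0%).

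**Sensitivity to the denominator.** Maternal endpoints may use more pregnancies than the primary analysis. If the planned minimum of 2,037 were all analysed (about 1,018 per group), power for pre-eclampsia at 3.5 points would be 67% for a rise and 80% for a fall. Women who change basal insulin or are not on basal insulin leave the secondary comparisons too (summary and 5.1), so the analysed share of any given enrolment is smaller.

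**The case against.** The strongest reply is that low power for the secondary endpoints cannot be derived from the protocol. The 3.5 points belong to the composite, and the doubling is an outside choice. This stands. A reader might combine the low entries of both scenarios and infer that the protocol's own rates leave the secondary endpoints generally underpowered, at 20 to 57%. The documents do not support that: it takes an absolute difference for common outcomes and a ratio for a rare one. Held to one rule, the picture is mixed. At 3.5 points both death endpoints reach about 80% or more, and at a doubling the common outcomes do.

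A reader might also extend the figures to spontaneous abortion. That fails. The 611 are pregnancies past 22 completed weeks, whereas spontaneous abortion is defined as occurring before that. The 15–26% in section 3.1 is a first-trimester risk in women with elevated glucose, and entry is allowed up to 16 weeks. Neither denominator nor rate can be taken from the protocol, so I give no figure.

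Continuous endpoints may well be adequately powered. If all 611 per group have data, a difference of 0.2 standard deviations gives Φ(0.2 × √(611 / 2) − 1.96) = Φ(1.54), about 94%.

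Finally, section 14.1 is open about its basis, section 5.4 calls the study exploratory, and section 14.4 already plans confidence intervals. Nothing says that a non-significant result will be reported as absence of harm. These points reduce the consequence. They do not make the statement in 5.2 true, and an exploratory label sits badly beside it.

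**Conclusion.** The claim in section 5.2 is wrong as written for the secondary endpoints: the document contains no calculation behind it. This is an overstatement, not an arithmetic error, since 1,833, 1,222 and 2,037 all hold up for the composite.

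How far the claim misses depends on the endpoint and on effect sizes that have to be assumed. The clearest shortfalls are a 3.5-point rise in pre-eclampsia (44%), a 3.5-point change in macrosomia (26 to 28%) and a doubling of neonatal death (20%, so missed about four times in five). Perinatal death is borderline, at 68 to 80%. These figures rest on the rates in section 3.1, 611 analysable pregnancies per group and the unadjusted Fisher test. They do not show that every secondary endpoint is underpowered.

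**What to change.** 1. Section 5.2: limit the power statement to the primary endpoint by deleting the words 'and secondary'.
2. Section 14.3: state that the study was not sized for the secondary endpoints. For the key secondary proportions, give the difference detectable with about 80% power at 611 per group, with baseline rate, test and denominator labelled as assumptions. Examples: pre-eclampsia 10% to about 15.5%, perinatal death 3% to about 6.5%, neonatal death 0.9% to just over 3.2%.

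Spontaneous abortion needs its own denominator and rate before a figure can be given. No change to section 14.4 is needed.

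The cost is a few sentences. Enrolment, data collection and analyses are unchanged. The downside is a less favourable stated property for the secondary endpoints.

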### **5.3 Treatment of patients**

Patients will be treated according to routine clinical practice at the discretion of the treating physician.

### **5.4 Limitation of study design and data sources**

Due to the exploratory nature of the study, the results will contribute to the current knowledge regarding treatment of pregnant women with both insulins and other injectable antidiabetic treatment regimens. A substantial high number of patients in the registry will enable confirmation of existing evidence from clinical studies and a generation of new hypotheses with respect to the long-term safety of Levemir® and other injectable antidiabetic treatment regimens in pregnant women with DM and their infants.

A heterogeneous patient population and different local requirements with regard to the routine patient management may limit the explanatory power of the study results if not well-adjusted in the analysis part. Heterogeneity will, however, be minimal in the present registry as the study sites have many similarities with regard to standard routine procedures in the treatment of pregnant women with DM. Confounding factors and other relevant background covariates will be collected at the baseline visit in order to adjust for relevant factors in the statistical analysis.

Protocol  
Study ID: NN304-4016  
UTN No: U1111-1132-9442  
EU PAS No.: ENCEPP/SDPP/4137

~~CONFIDENTIAL~~

Date: 08 September 2017  
Version: 6.0  
Status: Final  
Page: 21 of 60

**Novo Nordisk**

Results from statistical analysis may be biased if not all pregnancies are registered in the Diabetes Pregnancy Registry, particularly if data is only entered when the patient experiences an ADR/SAE. In order to minimise the risk of such bias the physician must ensure that all registered pregnancies regardless of treatment regimens in the specific clinic are enrolled in the Diabetes Pregnancy Registry unless the women do not want to participate (do not sign the informed consent form).

## 6 Study population

Women with DM, who are pregnant and are treated with Levemir® or other injectable antidiabetic treatment regimens, will be invited to participate in the Diabetes Pregnancy Registry. In order to obtain as much information as possible within an appropriate timeframe, women who have a positive pregnancy test, are diagnosed with DM prior to conception, and who have not changed basal insulin or other injectable antidiabetic treatment product (for those not treated with basal insulin) 4 weeks prior to and following conception will be included in the Diabetes Pregnancy Registry.

### 6.1 Number of patients to be studied

Estimated number of patients to be included during the recruitment period: minimum: 2,037

Recruitment will close once it is secured that 611 patients treated with Levemir® are eligible for the primary analysis.

Based on sample size calculations (Section 14) the number of pregnancies needed for the primary endpoint calculations is 1,222 pregnancies with information on the primary endpoint pregnancy outcomes:

- perinatal death
- neonatal death
- liveborn infant with 1 month follow up (irrespective if there is a malformation or not)

Liveborn infants will be followed up until 1 year with the aim of collecting data for the secondary endpoints.

It is expected that approximately 60% of the included pregnancies will be fulfilling the criteria for primary endpoint calculations, as 40 % are assumed to be excluded or used for secondary endpoints. These 40% of subjects are assumed to consist of subjects who experience one or more of the following: abortion (spontaneous or induced), change in basal insulin treatment, treatment with other antidiabetic treatment regimens, or lost to follow-up.

Therefore, it is calculated that a minimum of  $(1,222/60*100)$  2,037 patients are to be included in the study.

Note that the study plans to include a minimum of 2,037 patients treated with injectable antidiabetic treatment regimens, but that only women treated with Levemir® and other basal insulins will be included in the primary analyses.

## 6.2 Inclusion criteria

For an eligible patient, all inclusion criteria must be answered “yes”.

1. Informed consent obtained before any data collection
2. Woman with a positive pregnancy test
3. Diabetes mellitus type 1 or 2, diagnosed prior to conception
4. Currently treated with Levemir® or other injectable antidiabetic treatment(s)
5. Unchanged basal insulin or other injectable antidiabetic treatment product (for those not treated with basal insulin) 4 weeks prior to and following conception

An eligible woman may be included in the Diabetes Pregnancy Registry more than once, should the pregnancies occur within the recruitment period.

